- To determine if a 10 day delayed introduction of CNI affects the risk of graft rejection.
- Determine patient survival at 6 months post-transplant and compare survival rates between the two groups.
- Determine graft survival at 6 months post-transplant and compare graft survival rates between the two groups.
- Determine the incidence of AEs and SAEs in each group.

INVESTIGATIONAL PLAN:

A. Overall Study Design

This is a 24-month, Phase II, multi-center, two-arm, randomized study of adult patients receiving a single organ liver transplant from a deceased donor; the purpose being to determine the efficacy of Thymoglobulin® induction and delayed initiation of CNI in the long-term preservation of renal function after liver transplantation. This study is based on the outcomes of an earlier phase I pilot study which was performed at the Cleveland Clinic.

Study subjects will be asked to sign the Informed Consent at the time of admission for liver transplantation at Cleveland Clinic, and three other transplant centers, (University of Cincinnati, Medical College of Wisconsin, and Cleveland Clinic Weston, Florida), prior to OLT and prior to any study procedures, (that are not SOC), being performed. All subjects should be familiar with the Informed Consent and its content, and have been given opportunity to have their questions answered about the study, prior to signing the Informed Consent.

The length of the study will be approximately 24-36 months to allow for recruitment, and approximately 12 months of ongoing follow-up after the last patient is enrolled. A total of 110

subjects will be randomized (1:1) into one of two groups, 55 subjects per group. Subjects randomized to Group 1 will receive Thymoglobulin® induction, (4.5 mg/Kg, in 3 doses of 1.5 mg/Kg/dose), and delayed initiation of CNI, (to begin on Day 10 post LT). Subjects randomized to Group 2 will receive will receive early CNI initiation, (to be started no later than Day 2 post LT), and no Thymoglobulin® induction, (**or any other antibody**). In addition, all subjects will receive Mycophenolate Mofetile (MMF) and Corticosteroid immunosuppression as stated in Table 1.

Table 1: Immunosuppression Protocol

PHASE II RANDOMIZED 2-ARM MULTI-CENTER STUDY		
Treatment	GROUP/ARM 1 Thymoglobulin® + Delayed CNI	GROUP/ARM 2 Early CNI Group
Thymoglobulin®	Thymoglobulin® 1.5 mg/kg/dose Day 0, 2, and 4 (Total 4.5 mg/kg)	None
Tacrolimus	Start on post-transplant Day 10	Start no later than 48 hours post-transplant

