Mycophenolate mofetile	1000 mg BID start on day one post-transplant	1000 mg BID start on day one post-transplant
Corticosteroids	As per Transplant Center Immunosuppression Protocol - Taper off between 21 days-6 months post LT	As per Transplant Center Immunosuppression Protocol - Taper off between 21 days-6 months post LT

The Data Safety Monitoring Board (DSMB) will review the data on the first 30 subjects who have completed 30 days study enrollment.

Primary Endpoints:

- The incidence of AKI at 30 days post-transplant.
- Serum creatinine and eGFR at 30 days post-transplant.

Secondary Endpoints:

- The incidences of acute cellular rejection, (ACR), at 30 days post-transplant.
- Patient survival at 6 months post-transplant.
- Graft survival at 6 months post-transplant.
- The incidences of AEs and SAEs.

The primary endpoint for the study is a composite renal endpoint of Acute Kidney Injury, (**stages 2 to 3**), at 30 days post OLT. The staging of AKI will follow the classification system proposed by the Acute Kidney Injury Network (AKIN) depicted in **Table 2**.²⁶

TABLE 2: Classification / Staging for Acute Kidney Injury (AKI)

Classification/Staging System for Acute Kidney Injury ²⁶		
Stage:	Serum Creatinine Criteria	Urine Output Criteria:
1	Increase in serum creatinine of ≥ 0.3 mg/dL, (≥ 26.4 $\mu\text{mol/L}$), or an increase of $\geq 150\%$ to 200% , (1.5 to 2-fold), from baseline.	Less than 0.5 mL/kg per hour for more than 6 hours
2	Increase in serum creatinine of $> 200\%$ to 300% , (>2 to 3-fold), from baseline.	Less than 0.5 mL/kg per hour for more than 12 hours
3 ^a	Increase in serum creatinine to more than 300% , (>3 -fold), from baseline, (or serum creatinine of ≥ 4 mg/dL, [≥ 354 μmol], with an acute increase of ≥ 0.5 mg/dL, [44 $\mu\text{mol/L}$].	Less than 0.3 mL/kg per hour for 24 hours, or anuria for 12 hours.

^aOnly **one criterion** (creatinine or urine output) must be fulfilled to qualify for a stage. Individuals receiving renal replacement therapy (RRT) are considered to have met the criteria for **Stage 3** irrespective of the stage they were in at the time of RRT.

B. Patient Population

Study participants will be recruited from the Liver Transplant Programs at Cleveland Clinic, Cleveland, Ohio; University of Cincinnati, Cincinnati, Ohio; Medical College of Wisconsin Milwaukee, Wisconsin, and Cleveland Clinic Weston, Florida

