A randomization schedule will be generated and kept by each transplant center, after approval of the protocol by the Cleveland Clinic IRB, and each participating center's respective IRB, and prior to Study Start-up. Randomization numbers will be assigned in the order in which subjects qualify for treatment, not in the order of study subject enrollment.

Subject randomization will be performed provided the patient has signed the Informed Consent AND met all Study Entry Criteria, (Inclusion and Exclusion), **AND is "Enrolled" into the Study. Randomization will be performed within 6 hours of the patient's arrival to the Intensive Care Unit, (ICU),** after the transplant procedure. Subjects will be randomized in a 1:1 fashion to receive delayed CNI with 4.5 mg/Kg Thymoglobulin® [Group 1], or early CNI therapy [Group 2]. All subjects will receive maintenance therapy with MMF and corticosteroids.

G. Early Patient Withdrawal/Study Treatment Discontinuation

Subjects may voluntarily withdraw from the study or be withdrawn from the study, at the discretion of the investigator, at any time. A patient should be withdrawn from the study if the investigator believes that continuation would be detrimental to the patient's well-being. Reasons for **Study Treatment Discontinuation / Early Patient Withdrawal** are:

- Death after consent, but prior to randomization.
- Graft loss and/or re-transplantation.
- Pregnancy.
- Withdrawal of informed consent, (subject's decision to withdraw for any reason).

- Any clinically significant AE/SAE(s), laboratory abnormality, and/or incurrent illness which, in the opinion of the investigator, indicates that continued treatment with study therapy and/or further participation in the study, (including obtaining vital status of the subject and allograft), is not in the best interest of the subject.
- Unsatisfactory therapeutic effect (e.g. repeated acute rejection).
- Termination of the study by the investigating center or withdrawal of funds by Sanofi.
- Significant protocol violation.
- Protocol deviation resulting in significant patient safety risk.
- Subjects who for any reason cannot be followed and/or are unable to meet the requirements of the protocol.

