from the study. Information will be collected on serum creatinine levels, urea, eGFR, rejection episodes, graft loss/re-transplant, malignancies, opportunistic infections, patient survival and immunosuppressive therapy.

Subjects who did not complete the planned Thymoglobulin® course will be followed for any SAE(s) occurring within 30 days following the last dose of Thymoglobulin®. **These SAE(s) will be reported on the (MedWatch SAE Form) and UPLOADED to the Sanofi PV Portal, and faxed to Cleveland Clinic PI – “Attention: [name]” at [contact], within 24 hours of Study Site discovery/notification.** Since subjects will be followed even after discontinuation of the Study Drug, the **Study Completion CRF** should only be completed at 30 days, and Month 12 or earlier if the subject can no longer be followed. The following reasons are potential causes for premature discontinuation of study: graft loss, death, lost to follow-up and withdrawal of consent.

I. Emergency Un-Blinding of Treatment Assignment

This is an open-label study.

J. Study Completion and Post-Study Treatment

A Study Completion CRF should be completed at Month 12. The Investigator also must provide follow-up medical care for all patients who are prematurely withdrawn from the study, or must refer them for appropriate ongoing care. In addition, investigators will be asked to provide, for each randomized patient, a one-year follow-up data to describe patient survival, graft survival, acute rejection, current immunosuppressive regimen, recurrence of hepatitis C and renal function.

EFFICACY AND SAFETY ASSESSMENTS:

A. Renal function

Renal function will be assessed by estimated Glomerular Filtration Rate (eGFR), using the MDRD 4-variable equation. Serum creatinine will also be used as a parameter for determination of renal function at each Study Visit. Subjects will be classified for each occurrence of AKI according to the criteria in **Table 2**. Serum creatinine and weight must be recorded on the Study Visit CRF. All subjects will have their eGFR assessed at baseline, **Month 1, 3, 6, 9 and Month 12 post-transplant.**

B. Acute Cellular Rejection

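### The adverse-event withdrawal reason permits ending collection of vital and graft status, which contradicts the follow-up asked for elsewhere and could leave informative gaps in the 6-month survival endpoints

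*Combined protocol and SAP*

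**What the plan says.** Investigational Plan, section G (Early Patient Withdrawal/Study Treatment Discontinuation) says a subject may "be withdrawn from the study, at the discretion of the investigator, at any time". One listed reason is a clinically significant adverse event, laboratory abnormality or illness which, in the investigator's opinion, means that study therapy and/or further participation, "including obtaining vital status of the subject and allograft), is not in the best interest of the subject". Another listed reason is "Graft loss and/or re-transplantation".

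Two secondary endpoints rest on exactly these data: "Patient survival at 6 months post-transplant" and "Graft survival at 6 months post-transplant". The objectives are comparative. Study Objectives, section B has "Determine patient survival at 6 months post-transplant and compare survival rates between the two groups", with a matching objective for the graft.

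Other sections point the other way:

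- Other Medications/Therapies, section J (Study Completion and Post-Study Treatment): "investigators will be asked to provide, for each randomized patient, a one-year follow-up data to describe patient survival, graft survival, acute rejection".
- The end of Investigational Plan section G separates stopping treatment from leaving the study. Other Medications/Therapies, section H keeps patients who stop Thymoglobulin early in follow-up, including for graft loss and survival.
- Section H also lists the potential causes of leaving the study early. Adverse events are not among them.
- Data Collection, section D (Handling of Missing Values) starts from the premise that subjects are followed for renal function, graft loss or survival status.

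**The concern.** The parenthesis in section G extends withdrawal from treatment and visits to the outcome itself. Reading vital and graft status from the transplant record exposes the patient to nothing, so it is hard to see what patient interest would be served by stopping it. The decision is one of opinion, made with the arm known because the trial is open-label, and it is triggered by illness. Patients withdrawn on this ground can be expected to carry a higher risk of death or graft loss than those who stay, so missing status would be informative.

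At stake is the check on the renal strategy. The research hypothesis claims similar patient and graft survival, and the DSMB is to assess death and graft loss. Efficacy and Safety Assessments, section C counts death as graft loss, so one uncollected death affects both survival endpoints. The day-30 primary endpoints are not the subject of this point.

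**Working it through.** **1. Which events could go uncollected.** Deaths and graft losses are reported as serious adverse events (Efficacy and Safety Assessments, sections C and D). Under AE/SAE Reporting, section B:

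- from randomization to 30 days after participation stops, every serious adverse event is reported, whatever its cause;
- after that, for patients withdrawn early, up to 12 months from randomization, only if a relationship to the study is suspected.

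As an illustration, take withdrawal on Day 14 and Month 6 as Day 180. Unconditional reporting ends on Day 14 + 30 = Day 44. For the remaining 180 − 44 = 136 days, a death or graft loss judged unrelated reaches the database only through the one-year request in section J. Section G permits the investigator not to obtain that same information.

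**2. How such a patient would be analyzed.** Data Collection, section D gives imputation rules for Day 30 values and baseline creatinine only. Study Endpoints, section C has a rule for the composite that covers loss to follow-up and withdrawn consent only. Neither says how an investigator-withdrawn patient enters the 6-month survival analyses.

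**3. Possible size.** The plan gives no withdrawal rate and no figure on this point to reproduce. Inputs:

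- n = 55 per arm (Investigational Plan, section A).
- Event rates, as an assumption: 6-month patient survival 91% and graft survival 84%, from the normal-renal-function group of the retrospective series of 298 patients (Introduction, section C). Then 55 × 0.09 = 4.95, about d = 5 deaths, and 55 × 0.16 = 8.8, about d = 9 graft losses, per arm.
- w = number of events missed in one arm, assumed to be 1 to 3.

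True survival is 1 − d/55. If the w patients are censored early or excluded, the estimate is 1 − (d − w)/(55 − w). If they stay in the denominator with no event recorded, it is 1 − (d − w)/55.

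| Missed deaths (d = 5, true 90.9%) | Censored early | Shift (points) | Kept, no event | Shift (points) |
|---|---|---|---|---|
| 1 | 1 − 4/54 = 92.6% | 1.7 | 1 − 4/55 = 92.7% | 1.8 |
| 2 | 1 − 3/53 = 94.3% | 3.4 | 1 − 3/55 = 94.5% | 3.6 |
| 3 | 1 − 2/52 = 96.2% | 5.2 | 1 − 2/55 = 96.4% | 5.5 |

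For graft survival (d = 9, true 83.6%), missing 1, 2 or 3 losses under early censoring shifts the estimate by 1.5, 3.2 or 4.8 points.

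**4. Against the precision of the comparison.** With equal true rates and nothing missing, the 95% half-width for the difference is 1.96 × √(2p(1 − p)/55). With p = 5/55 this is 10.7 points; with p = 9/55 it is 13.8 points. If 3 deaths are missed in one arm only, the spurious difference is 5.2 points (95% CI −4.0 to 14.5). Only losing all 5 deaths from one arm moves the interval off zero (9.1 points, 1.5 to 16.7).

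**The case against.** The strongest reply is that the plan largely covers this already. Section J asks for one-year survival on each randomized patient, straight after a sentence about prematurely withdrawn patients, and one-year data would normally show status at 6 months. Patients who only stop treatment stay in follow-up. Section H does not list adverse events as a cause of leaving the study. Deaths soon after withdrawal, which are the most likely ones in very ill patients, are reportable for 30 days regardless of cause. The clause in section G is also worded with and/or, so ending status collection is the outer limit of a discretion and not its normal use.

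Most of this stands, and it limits the point to a possible loss of later, unrelated events. It does not remove the contradiction. Section J is a request, while section G is an explicit permission to stop, so a site could rely on section G and be within the protocol. Section H's follow-up rule concerns stopping Thymoglobulin, which only Arm 1 receives, and does not address leaving the study.

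The size is also open to challenge. Missing 1 to 3 of 5 deaths is an assumption, and the early-censoring formula removes only patients who later die. Removing withdrawn survivors as well shrinks the bias slightly: one missed death plus three censored survivors gives 1 − 4/51 = 92.2%, against 92.6%. That criticism is fair, and the figures should be read as a range for illustration.

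**Conclusion.** The contradiction is real and should be resolved. Section G permits what section J and the missing-data section assume will not happen, and serious adverse event reporting is only a partial backstop. A death or graft loss more than 30 days after withdrawal and judged unrelated may go uncollected, and that missingness would be informative. If 1 to 3 of 5 deaths in an arm of 55 were missed and those patients censored early, estimated survival would be about 1.7 to 5.2 points too high. This rests on assumed event and missed-event counts. A false significant difference is unlikely. The practical risk is that a modest survival deficit looks like similarity.

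A reader might infer two stronger things:

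- That the plan drops these deaths by design, or censors such patients. It does not: section J asks for their outcome, early serious adverse events are reportable, and no text says that investigator-withdrawn patients are censored.
- That the comparison is tilted toward the Thymoglobulin arm because of its adverse-event profile. The documents report adverse events, not withdrawals, and describe the events as generally manageable or reversible. The direction between arms is unknown.

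**What to change.** In Investigational Plan section G, delete from the adverse-event reason the parenthesis that extends withdrawal to vital and allograft status. State instead that vital status, re-transplantation and event dates through Months 6 and 12 are taken from the transplant record for every randomized patient in both arms, whatever the reason for withdrawal, unless the patient withdraws consent to data collection. Add that these patients are included in the survival analyses as randomized. Align the wording of Other Medications/Therapies sections H and J and of Data Collection section D with this.

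The change concerns data collection only and alters no treatment or stopping rule. The cost is one clause and a little extra record abstraction. No visit or procedure is added, because Study Assessments, section D already has early-withdrawn patients continuing routine post-transplant laboratory follow-up.

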Group 1/Arm 1: [Thymoglobulin® Induction (4.5mg/Kg – Total Dose – administered in 3 Infusions of 1.5mg/Kg per Infusion {**Each dose of Thymoglobulin® to be corrected (rounded up or down to the nearest 25mg dose) – the maximum single dose not to exceed 150mg**}, on Day(s) 0, 2, and 4 post OLT)], **plus** Delay CNI initiation – CNI start on Day 10 post OLT, **plus** MMF and Corticosteroids.

Group 2/Arm 2: [Early CNI – CNI initiation by Day 2 post OLT], **plus** MMF and Corticosteroids. No Thymoglobulin®/or any other Antibody induction.

B. Dose Adjustments / Dose Holds / Discontinuation:

Thymoglobulin® dose adjustments should be based on AEs / SAEs.

The Following will Necessitate a Dose Reduction, and/or Discontinuation of Thymoglobulin® Infusion [Dose 2 and/or Dose 3]:

- **Major/Severe Allergic Reaction or Anaphylactic Reaction** – all further Thymoglobulin® Infusions are to be **DISCONTINUED** – patient will be taken “Off Study”.
- **ANC less than 1200 cells/μL** - Reduce dose by 50%
- **ANC less than 800 cells/μL** - Hold dose and re-evaluate the following day
- **Platelet count: <20000** give half of the dose or delay the dose for 24h and re-check. Infuse platelets if platelet count is still <20000 after 24h of delay before Thymo infusion. **Do not infuse if platelet count is <10000.**

INFUSION REACTION:

- **All patients are to be pre-medicated with [corticosteroids, antihistamine, acetaminophen (per institutional standard)], prior to each Thymoglobulin® Infusion, (in order to minimize the incidence of “infusion reaction”).**
- **In the event of Thymoglobulin® Infusion Reaction [fatigue, headache, nausea, vomiting, abdominal pain, fever, chills, pruritus, urticaria] – INTERRUPT THE INFUSION AND INFORM THE PHYSICIAN BEFORE RESUMING THE INFUSION.**
- **The infusion may be resumed at a 50% decreased flow rate (with a maximum length of infusion of 8 hours):**

AS CLINICALLY INDICATED, BASED ON:

- **The patient’s reaction**
- **The clinical decision of the Physician/Investigator at each Center**
- **Each center’s “Institutional Standard”**

Vital Signs should be checked and the patient assessed every 15 minutes until the infusion is completed. The Infusion Reaction is to be documented on the Infusion Record and the AE CRF.

SEVERE INFUSION REACTION:

[Hypotension / Shortness of Breath / Bronchospasm / Anaphylaxis]

- **STOP THE INFUSION AND NOTIFY THE PHYSICIAN**
- **FOLLOW INSTITUTIONAL PROTOCOL FOR SEVERE DRUG REACTION**

C. Treatment Blinding

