In the event of suspected acute liver allograft rejection, **an allograft biopsy MUST be performed PRIOR to the initiation of anti-rejection therapy**. Whenever possible, anti-rejection therapy should be postponed until a histological diagnosis of rejection is confirmed. These biopsies will be read locally at each clinical center and the histological lesions will be graded according to the **Grading of Acute Liver Allograft Rejection, (Banff)**. Biopsy results from the local pathologist are to be recorded on the Liver Allograft Biopsy CRF. Patients experiencing a Biopsy Proven Acute Rejection (BPAR) episode should be treated in accordance with the Study Site standard practice. Treatment is to be consistent for all subjects at each respective Study Site. Details of treatment of rejection will be recorded on the appropriate CRF. A biopsy for suspected rejection will be performed based on clinical/biochemical information and judgment of the Investigator(s).

G. Diagnosis and Treatment of HCV:

For suspected HCV infection, an allograft biopsy will be performed prior to initiation of any anti-HCV viral therapy. The biopsy will be read locally, at each Study Site, and the histological lesion(s) will be graded. The biopsy results, as reported by the Study Site local pathologist, will be recorded on the Liver Allograft Biopsy CRF. Patients experiencing a biopsy proven recurrence of HCV infection are to be managed following the local standard practice in a consistent manner within the center for all subjects. Details of treatment of HCV will be recorded on the appropriate CRF.

H. Study Drug (Thymoglobulin®) Discontinuation

In the absence of medical contraindication or significant protocol violation, every effort will be made to continue Thymoglobulin® dosing. Reasons for Thymoglobulin® (Study Drug) discontinuation will be recorded on the appropriate CRF. Reasons for Thymoglobulin® (Study Drug) discontinuation are:

- Death
- Graft Loss
- Withdrawal of Informed Consent
- Clinically significant AEs/SAEs
- Unsatisfactory therapeutic effect
- Significant protocol violation
- Protocol deviation resulting in significant patient safety risk

All subjects discontinuing Thymoglobulin® prior to completing the target total dose will continue to be followed in order to obtain follow-up information, and should not be considered withdrawn

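### The off-study rule for severe Thymoglobulin reactions contradicts the protocol's own follow-up rule and can lose Day-30 renal data in Arm 1 only

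*Combined protocol and SAP*

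**What the plan says.** All references are to the combined protocol and SAP.

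- **Study Treatments B (Dose Adjustments / Dose Holds / Discontinuation):** a major or severe allergic or anaphylactic reaction ends all further Thymoglobulin infusions, and the "patient will be taken “Off Study".
- **Other Medications/Therapies H (Study Drug Discontinuation):** the reasons for stopping the drug include "Clinically significant AEs/SAEs" and "Unsatisfactory therapeutic effect". The section continues: "All subjects discontinuing Thymoglobulin® prior to completing the target total dose will continue to be followed in order to obtain follow-up information". Such subjects "should not be considered withdrawn" from the study, and creatinine, eGFR, rejection, graft and survival data are to be collected on them.
- **The same section H, on the Study Completion form:** it gives "potential causes for premature discontinuation of study: graft loss, death, lost to follow-up and withdrawal of consent".
- **Other Medications/Therapies J (Study Completion):** investigators are asked for one-year data on each randomised patient, covering survival, graft, rejection and renal function.
- **Investigational Plan G (Early Patient Withdrawal/Study Treatment Discontinuation):** one list serves both purposes. It includes graft loss, protocol violation and "Unsatisfactory therapeutic effect (e.g. repeated acute rejection". It also has a clause under which an adverse event may end participation, even the collection of vital status. G adds that withdrawal from treatment does not imply withdrawal from the study, but does not say which reasons do which.
- **Data Collection D (Handling of Missing Values):** Day-30 values are expected to be missing only through death, withdrawn consent or loss to follow-up, and are filled by LOCF.

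**The concern.** Stopping a drug and leaving a trial are different events, and the comparison of randomised groups depends on keeping them apart. Study Treatments B joins them for one event that can occur only in the arm receiving Thymoglobulin. A site that follows it would stop collecting study data on a reacting patient; a site that follows section H would not.

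What is at stake is later information: Day-30 AKI, creatinine and eGFR (the primary endpoints), six-month patient and graft survival, and twelve-month outcomes. Safety follow-up can also be cut short, because for patients withdrawn early the extended SAE reporting, to 12 months, applies only where a relationship to the study is suspected. Loss of data that depends on a treatment-related event, and that can occur in one arm only, cannot be assumed to be at random. No analysis population is defined that would settle how such patients are counted; intent-to-treat appears only in the abbreviation list.

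**Working it through.** **1. The plan's own figure.** The sample size is not in dispute. Welch's t-test with difference 0.32, SDs 0.51 and 0.51, two-sided 5% and 55 per arm has noncentrality 0.32 / √(0.51²/55 + 0.51²/55) = 3.29 and power 90.3%. The stated total of 110 for 90% power reproduces, as do the other entries in the sample-size table.

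**2. The rules side by side.**

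| Event | Text that ends study participation | Text that keeps the patient in |
|---|---|---|
| Severe reaction to Thymoglobulin | Study Treatments B | H: adverse events are a listed drug-stopping reason, and all who stop are followed |
| Graft loss | H, Study Completion form | J: one-year data on each randomised patient |
| Repeated rejection, protocol violation | G, if the joint heading is read as study withdrawal | G, if read as treatment withdrawal |

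The first row is a direct contradiction. The off-study phrase is hard to read as another way of saying off drug, because the same sentence has already stopped the drug. Other Medications/Therapies A, on tacrolimus neurotoxicity, also says that such a patient need not leave the study, so the protocol treats removal as a separate step. The second row is an inconsistency. The third is ambiguity.

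**3. Consequence for Day 30.** Doses fall on Days 0, 2 and 4, so a removal under this rule would come in the first days. The carried-forward creatinine could be the pre-transplant value, which shows no change and hence no creatinine-defined AKI. It could also be an early post-transplant value, since the renal function section refers to creatinine at each study visit and sites run their own labs. The documents do not say which.

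**4. Illustration of size.** The documents give no rate for severe reactions or for withdrawals. Assume a 30% AKI rate in Arm 1, that is 0.30 × 55 = 16.5 events.

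*Removed patients excluded, all of whom would have had AKI:* observed rate = (16.5 − k) / (55 − k).
- k = 1: 15.5/54 = 28.7%, 1.3 points low
- k = 3: 13.5/52 = 26.0%, 4.0 points low
- k = 5: 11.5/50 = 23.0%, 7.0 points low

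With k = 5, an assumed rate of 20% gives (11 − 5)/50 = 12.0%, 8.0 points low; 40% gives (22 − 5)/50 = 34.0%, 6.0 points low. For exclusion these are upper bounds at each k.

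*Removed patients excluded, with average risk:* (16.5 − 0.3k) / (55 − k) = 30%. The expected bias is zero.

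*LOCF, denominator still 55:* each misclassified patient moves the rate by 1/55 = 1.8 points. Three AKI cases scored as none give 13.5/55 = 24.5%. Three recovered patients scored as AKI from an early peak give 19.5/55 = 35.5%.

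**5. Power.** Losing 1, 3 or 5 Arm 1 patients at SDs 0.51/0.51 gives 90.1%, 89.5% or 88.9%. The issue is not power.

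**The case against.** The strongest reply is that the off-study phrase is one loose line outweighed by the rest of the document. Section H requires renal, rejection, graft and survival data after the drug is stopped. Section J asks for one-year data on everyone randomised. The laboratory section says that patients withdrawn early keep having routine labs, and the missing-data section expects follow-up for renal function. The safety sections also call immediate serious allergic reactions and anaphylaxis very rare, and premedication is required, so few patients may be affected.

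Much of this stands. It limits the likely size and shows that the intended policy was probably continued follow-up. It does not remove the contradiction: the off-study rule is the more specific one, a major or severe allergic reaction is not defined, and continued routine labs are not the same as recorded study data.

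A reader might go further and infer that graft loss and repeated rejection selectively remove bad outcomes. The documents do not support that. Both graft loss and biopsy-proven rejection are recorded and reported when they occur, so only later data are at risk. The list of causes for leaving the study in section H contains graft loss but neither poor effect nor protocol violation. Section H's follow-up rule concerns Thymoglobulin, whose last dose is scheduled for Day 4, so later graft loss or rejection does not contradict that rule. For repeated rejection, the joint heading in Investigational Plan G can be read as ending treatment only.

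**Conclusion.** The contradiction between Study Treatments B and section H is established from the text alone and should be corrected. The graft-loss wording in section H is at odds with section J, and Investigational Plan G needs clarifying.

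A reader might also infer that the rule favours Arm 1 by about 4 points on AKI. That does not follow. The figure needs three reactors among 55 who all go on to AKI, although the protocol calls immediate serious reactions very rare, and it drops them from the denominator although the plan specifies LOCF for missing Day-30 values. Under LOCF the direction depends on which creatinine is carried forward. The supportable statement is narrower: the rule creates missing Day-30 renal data that can arise in Arm 1 only and that the missing-data section does not allow for. The size and direction of any bias are unknown. The range of 1.3 to 7.0 points is an illustration that rests on an assumed 30% AKI rate, one to five exclusions and AKI in every excluded patient.

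**What to change.** Reconcile Study Treatments B, Investigational Plan G, Other Medications/Therapies H and the pregnancy section, so that stopping study drug and leaving follow-up are separate decisions throughout:

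- Replace the off-study wording in Study Treatments B with wording that keeps the patient in study follow-up, in line with section H.
- State for each reason in Investigational Plan G whether it ends follow-up, and make the Study Completion list in H agree. The pregnancy section ends both treatment and participation, so it should also say what follow-up continues.
- Continue collecting at least creatinine/eGFR, AKI status, rejection, graft and patient survival after graft loss or drug discontinuation, unless consent to follow-up is withdrawn.
- State that all patients are analysed as randomised, and align the missing-data paragraph with the reconciled list.

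This takes no view on when treatment should stop. The cost is small: a wording amendment, and recording on the case report form labs that the laboratory section already says continue in routine care.
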